### **6.3 PATIENT SETS ANALYZED**

#### Randomized set (RS)

This patient set includes all patients that were assigned a randomization number within the IRT system.

#### Treated set (TS)

This patient set includes all randomized patients who were documented to have taken at least one dose of study medication.

The treated set will be used in all planned analyses

No per-protocol set is defined and no analysis is planned.

### **6.5 POOLING OF CENTRES**

This section is not applicable because centre/country is not included in the statistical model.

[figure not shown]
## **6.6 HANDLING OF MISSING DATA AND OUTLIERS**

[figure not shown]
### Exacerbations and vital status data

Patients will be followed up for exacerbation and vital status. Missing data for these endpoints will not be imputed. For each time to event analysis, patients who do not have a particular outcome will be censored (for details see [section 7.5.2](#)).

### AE data

Missing or incomplete AE dates are imputed according to BI standards (see “Handling of missing and incomplete AE dates” [\(2\)](#)).

## **6.7 BASELINE, TIME WINDOWS AND CALCULATED VISITS**

The study's treatment period is planned to have a duration of 360 days and includes 5 clinic visits, conducted every 3 months, interspersed with a telephone contact call 6 weeks between clinic visits. Twenty-one (21) days after the end-of-treatment (EOT) visit a follow-up visit will be performed.

Time windows will not be used. Variables that are collected at clinic visits will be analyzed by planned visit (e.g. for trough FEV1 in the sub-study). Exacerbation and time-to-event analyses are collected in real-time.

With regard to all efficacy assessments, the term "baseline" refers to the last observation obtained at visit 2.

For all other data, including relevant medical history, concomitant therapies, AEs, lab values, and vital signs, visit 1 will be classed as "baseline".

## **6.8 CALCULATION OF TIME TO EVENT**

The calculation of the time-to-event and the time that patients without an event were in the study (at risk) is described here.

### Day 1

The date of first administration of treatment is the reference for all time-related analyses.

### Date of event

In the exacerbation analyses, where a patient can have multiple events, the onset date of the first event will be used.

For death, the adverse event end date reported on the eCRF will be used as the final date of death.

### Last known date alive

The date of last known day alive is determined as the latest date among: the final vital status date (defined as the assessment date if alive, or date last known alive if 'unknown'), the date of first dose of study medication, the date of last drug administration, all the visit dates (including phone contact dates in which the patient was reached and follow-up contact dates) and start or stop dates of events reported on the adverse event forms.

If a patient dies, the date of death is the last date known alive.

[figure not shown]
**Survival time calculations:**

A. Actual treatment event analysis: Events (death or exacerbation) are counted in the actual treatment time to event analysis whenever they occur between the first dose of randomized treatment and one day after treatment discontinuation (i.e. during the actual treatment period) (see [section 6.1](#)).

Patients with no event observed during the actual treatment period will be censored at date of last dose of randomized study drug administration (i.e. treatment discontinuation) +1 day.

Time at risk:

- *Patients with event counted:* (<date of event> – <date of first drug administration> +1).
- *Patients without event counted:* (<date of last dose of study drug> – <date of first drug administration > +1) + 1 day wash-out

## 6.9 CALCULATION OF ANNUALIZED RATE

In all analyses of annualized\* rate of event, the length of the event will be subtracted from the extent of exposure or the length of the observation period because an additional event cannot occur during an event.

For the on-treatment analysis total exposure is calculated as follows:

$$\text{total exposure in patient years} = \frac{\sum \text{all patients' exposure}}{365}$$
$$\text{observed rate of event} = \frac{\sum \text{number of events}}{\sum \text{all patients' exposure} - \sum \text{duration of events}}$$

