## 5.1.2 Assessment of efficacy

### 5.1.2.1 Definition of moderate and severe COPD exacerbations

For the purpose of this study, a COPD exacerbation is defined as a complex of lower respiratory events / symptoms (increase or new onset) related to the underlying COPD, with duration of three days or more, requiring a prescription of antibiotics and / or systemic steroids and/or hospitalisation.

A complex of lower respiratory events / symptoms is defined as at least two of the following:

- Shortness of breath
- Sputum production (volume)
- Change in sputum colour
- Cough
- Wheezing
- Chest tightness

“Onset of exacerbation” will be defined by the onset of first recorded symptom. The “end of exacerbation” will be decided by the investigator based on clinical judgment.

Exacerbations will be classified as follows:

- Mild: a new prescription of maintenance bronchodilator only
- Moderate: patient receiving an exacerbation-related prescription of oral corticosteroids and/ or antibiotic not requiring hospitalisation.
- Severe: COPD-related hospitalisation including emergency room visit\*

To consider hospitalisation associated with COPD exacerbation, the information collected should include the start date of all COPD-related hospitalisations as well as the discharge date from the hospital or equivalent

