### 7.3 PLANNED ANALYSES

#### 7.3.1 Primary analyses

The primary analysis includes all randomised patients who are documented to have received any dose of study medication, i.e., the primary analysis is performed using the treated set.

The primary endpoint, i.e., annualised rate of moderate to severe COPD exacerbation will be analysed using a negative binomial model including the fixed, categorical effect of treatment

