## 7.6 DETERMINATION OF SAMPLE SIZE

Based on a recent publication on the SPARK study (Wedzicha, et al, Lancet, 2013) and data from a previous BI study [REDACTED], the rate ratio and hazard ratio of moderate to severe COPD exacerbation between T+O FDCs and Tio 5 are assumed to be 0.88.

Assuming an annualised rate of moderate to severe COPD exacerbation for Tio 5 to be 0.85, a 12-month fixed study duration, two-sided type I error rate of 0.01 and 90% power, the sample size depends on the dispersion parameter for the negative binomial distribution. [Table 7.6: 1](#) gives the sample size estimations for a range of the dispersion parameters. In addition, assuming a 15% loss of information in patient-years, the estimated power corresponding to the sample size is also provided in the last column in Table 7.6: 1 below.

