## 6. GENERAL ANALYSIS DEFINITIONS

### 6.1 TREATMENTS

As described in Section 4 of the revised CTP, patients will be randomized in equal allocation to one of two treatment groups delivered by the Respimat® inhaler:

- Tiotropium + olodaterol fixed dose combination (FDC) (5µg / 5µg) inhalation solution once daily
- Tiotropium (5 µg) inhalation solution once daily.

Table 6.1: 1 Treatments and their labels

Treatment	Short label
Tiotropium + olodaterol FDC (5 µg / 5 µg) inhalation solution	T+O 5/5
Tiotropium (5 µg) inhalation solution	Tio 5

The trial consists of a 360 days of treatment followed by a 21 day residual effect period.

For analysis purposes the following periods are defined:

- Planned study period  
The planned study period is defined as 360 days of treatment + 21 days of follow up after the administration of the first dose of trial medication according to the CTP flow chart.
- Planned treatment period  
The planned treatment phase is defined as 360 days of treatment + 1 day for wash-out according to the CTP flow chart.
- Actual treatment period  
The actual treatment period is defined as the interval from first in-take of study medication until 1 day after last in-take of study medication.
- On-treatment period  
The on-treatment period is defined as the interval from first in-take of study medication until 21 days after last in-take of study medication.

Patients that discontinue early will be monitored for exacerbations and vital status until they have reached the end of their planned study period.

Table 6.1:2 Analyses performed within each period

Types of Analyses to be performed	Periods			
	Actual treatment period (Treatment +1 day wash-out)	Planned treatment period (includes 1 day wash-out)	Planned study period (includes residual effect period of 21 days)	On-treatment period (includes residual effect period of 21 days after last drug intake)
Primary Exacerbation analysis	✓			
Sensitivity primary exacerbation analysis		✓		
Key secondary exacerbation analysis	✓			
AE safety analysis				✓

Patients will be analyzed according to the treatment group of the first treatment received. Potential treatment switcher scenarios caused by treatment misallocation will be discussed at the Blinded Report Planning Meeting (BRPM). After database lock (DBL) patients who fall into these discussed scenarios will be analyzed according to meeting decisions.

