## **7.4 PRIMARY ENDPOINT**

### Primary Analysis

As stated in section 7.3.1 in the revised CTP: “The annualized rate of moderate to severe COPD exacerbation will be analyzed using a negative binomial model including the fixed, category effect of treatment as well as the logarithm of the treatment exposure as an offset. [...] Moderate to severe COPD exacerbations occurring within 1 day (24 hours) after the last drug administration date, are included in the primary analysis”.

See [section 6.9](#) for calculation of observed rate.

Annualized rates of moderate to severe COPD exacerbations will be tested for equivalence between the two treatment groups T+O 5/5 and Tio 5. The hypothesis (H) test is:

$$H_{10}: RR = 1$$

vs.

$$H_{11}: RR \neq 1,$$

where  $RR = \frac{\lambda_{(T+O)}}{\lambda_{(Tio)}}$  and  $\lambda_{Tio}$  is the annualized rate for the patients in the Tio 5 group and  $\lambda_{T+O}$  is the annualized rate for the patients in the T+O 5/5 group and RR is the rate ratio between the two groups.

[figure not shown]
The hypothesis test will be evaluated using a two-sided  $\alpha=0.01$ . Ninety-nine (99)% confidence intervals will be obtained. Type III sums of squares will be produced.

The following SAS® code for the negative binomial model will be used:

```
proc genmod data=exac_negbin;
  class trt;
  model evtnum=trt/noint dist=negbin link=log offset=logdurs type3
  alpha=0.01;
  lsmeans trt/cl diff exp alpha=0.01;
run;
```

where TRT=treatment group and LOGDURS=log(exposure) as described in [section 6.9](#). The OFFSET=LOGDURS is used to account for different exposure, or observation periods per subject.

The primary analysis will be an actual treatment analysis performed on the treated set (TS) (see [section 6.3](#)). The exacerbation events will be only counted in this analysis if they occurred during the actual treatment period (see [section 6.1](#)).

[Section 9.1](#) details additional rules applied to the analysis of the primary endpoint.

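### SAP 6.9 subtracts the full length of each exacerbation from exposure, even days after last dose + 1 day, so a few treated patients could get an undefined offset and leave the primary model; the effect is small

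*SAP*

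**What the plan says.** - **Subtraction.** SAP 6.9 and protocol 7.3.1 use the same words: "the length of the event will be subtracted from the extent of exposure or the length of the observation period". The reason given is that a new event cannot start while one is in progress. The observed-rate formula in SAP 6.9 subtracts the summed event durations without limit. SAP 7.4 uses the log of the exposure described in 6.9 as each patient's offset in PROC GENMOD.
- **Counting window.** SAP 7.4: "The exacerbation events will be only counted in this analysis if they occurred during the actual treatment period". SAP 6.1: "The actual treatment period is defined as the interval from first in-take of study medication until 1 day after last in-take of study medication".
- **Event end.** Under protocol 5.1.2.1 the end of an exacerbation "will be decided by the investigator based on clinical judgment". Protocol 5.1.2.2 collects exacerbations to 52 weeks + 21 days, also in patients who stop early, so end dates beyond the window can be recorded. SAP 9.1 merges events that are at most 7 days apart, which can lengthen an event.
- **Analysis set.** Protocol 7.3.1: "The primary analysis includes all randomised patients who are documented to have received any dose of study medication". SAP 6.3 applies the treated set to all planned analyses.
- **Base denominator.** SAP 6.9 introduces its exposure formula as on-treatment, which SAP 6.1 defines as running to last dose + 21 days. SAP 7.7 defines exposure as stop date - start date + 1. The counting window, and the time at risk for event-free patients in SAP 6.8, run to last dose + 1 day.

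Nothing visible in SAP 6.8, 6.9, 7.4 or 9.1 cuts an event at the end of the window, sets a minimum exposure, or covers a result of zero or less.

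**The concern.** The reason for the subtraction covers only event days that lie inside the period being analysed. An event that starts in the window and ends after it has further days that were never in the denominator. A programmer who takes end date minus onset date would subtract those as well.

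Three things follow. If the event is at least as long as the patient's whole exposure, the log offset does not exist, and GENMOD omits the record and its event. If a few days remain, the patient stays in with too short a time at risk. A completer whose event is still open at the last dose also loses too many days.

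The first group matters most in principle. Every such patient has a counted exacerbation, so the omission depends on the outcome, would happen silently, and conflicts with the treated-set rule. The observed-rate formula sums over patients and would still count those events, so the descriptive table and the model would disagree. The hospitalisation rate uses the same model (SAP 7.5.2).

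**Working it through.** **Plan's own figures.** Protocol 7.6 takes "a 12-month fixed study duration, two-sided type I error rate of 0.01 and 90% power", a Tio 5 rate of 0.85 per year and a rate ratio of 0.88, hence 0.748 per year on T+O. With k the dispersion, N per arm = (2.576 + 1.282)² × (1/0.85 + 1/0.748 + 2k) / (ln 0.88)² = 910.5 × (2.5134 + 2k).

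- k = 0.625: 3427 (plan 3427)
- k = 0.7: 3564 (plan 3563)
- k = 0.8: 3746 (plan 3745)
- k = 0.9: 3928 (plan 3927)

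With 15% fewer patient-years, 3900 per arm gives 86.2% to 90.7% power (plan 86.1% to 90.6%). These figures reproduce and do not depend on the offset rule. They set the scale: about 3900 × 0.85 × (0.85 + 0.748) = 5297 expected events.

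**Day arithmetic.** First dose is Day 1. Window length W = last dose + 1 day - first dose + 1. Event length L = end - onset + 1. The literal offset is W - L. The proposed offset is W minus the event days after the onset day and on or before last dose + 1 day.

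| Case | Onset | Last dose | End | W | L | Literal W - L | Proposed |
|---|---|---|---|---|---|---|---|
| (a) stops early | 8 | 10 | 28 | 11 | 21 | -10 (undefined) | 11 - 3 = 8 |
| (b) stops early | 12 | 14 | 25 | 15 | 14 | 1 | 15 - 3 = 12 |
| (c) completer | 355 | 360 | 375 | 361 | 21 | 340 | 361 - 6 = 355 |

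Only (a) leaves the model. Case (b) stays in with 1 day, a personal rate of 365 per year.

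**Effect of the base denominator.** With SAP 7.7 exposure the literal results are 10 - 21 = -11, 14 - 14 = 0 and 360 - 21 = 339, so (b) is lost too. With last dose + 21 days they are 31 - 21 = 10, 35 - 14 = 21 and 381 - 21 = 360, and none is lost. That reading, however, adds 21 - 1 = 20 days per patient in which no event can be counted.

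**Size.** The documents give neither event length nor the share of events followed by stopping drug, so both are assumed. Two separate simulations used 3900 per arm and the plan's rates.

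- *Set 1* (dispersion 0.7, about 0.85 year mean exposure, 10 trials per scenario). With mean event length 14 days and 0%, 5% or 10% of events followed by stopping within 3 days, 2.5, 10.7 and 19.5 patients are lost. With 21 days and 10%, 35.9 are lost. That is 2/7800 = 0.03% to 36/7800 = 0.46%. The Tio 5 rate is 0.862 literal against 0.857 clipped (0.6% higher) at 14 days and 0%, and 0.865 against 0.859 (0.7% higher) at 21 days and 10%. The log rate ratio moves by 0.001 to 0.003. SE(log RR) in the 21-day case is 0.0346 against 0.0341, so 0.003 is under a tenth of one SE.
- *Set 2* (dispersion 0.8, median length 10 to 21 days, 3% to 10% stopping during an event, 10% per year other stopping, 4 trials per scenario). 5.5 to 20.5 patients are lost (0.07% to 0.26%). The rate is 0.3% to 0.9% higher and the rate ratio differs by at most 0.0006. With 8% stopping on Tio 5 and 3% on T+O, the losses are 6.25 and 1.5 patients, and the rate ratio is 0.8706 against 0.8705.

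In set 2 the literal fit used SAP 7.7 exposure and the clipped fit added the + 1 day. That day alone is 7800/365 = 21.4 patient-years, or 0.3% of 7191 in the shortest-event scenario. Part of the 0.3% to 0.9% therefore reflects the unclear denominator.

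Clipping the whole event, onset day included, still left about 1 to 2 patients at zero or less in set 2 (event running from Day 1 to the end of treatment). Leaving the onset day at risk removes this.

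**The case against.** **The documents never say outright that days after the window are subtracted.** Correct. It is the literal reading of an unqualified rule, and the stated reason points to days at risk only. But the formula in SAP 6.9 is equally unqualified, and code needs an explicit limit.

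**The situation should be rare.** Protocol 3.3.4.1 says that an exacerbation is not a reason for withdrawal and foresees interruptions such as hospital stays. This limits the numbers, and the larger losses above rest on undocumented stopping shares. The same section allows withdrawal for adverse events, and case (c) needs no early stop.

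**A safeguard exists.** SAP 6.1 plans a sensitivity analysis over the planned treatment period. Early stoppers who are followed up have a long denominator there, so non-positive exposure largely disappears. That does not repair the primary analysis.

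**Text may be missing.** The footnote marked at the word annualized in SAP 6.9 is not visible, so a handling rule cannot be ruled out.

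Three stronger readings are tempting and not supported:

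- A reader might infer that near-zero exposure also drops out. It does not; it enters with a large negative offset.
- A reader might infer that the rule biases the dispersion upward. The literal fits do give higher values than the clipped ones. Yet with a true value of 0.7, the 14-day, 0% case gave 0.701 literal and 0.681 clipped, so an error against the truth is not shown.
- A reader might infer that stopping which differs by arm endangers the comparison. In the 8% v 3% scenario the rate ratio barely changed.

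**Conclusion.** The point holds as a minor defect. Followed as written, the rule subtracts days outside the denominator and can remove treated patients with a counted event from the primary model. The base denominator also needs one definition.

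Under the assumed event lengths and stopping shares, about 2 to 36 of 7800 patients are lost, fitted rates are under 1% too high against a clipped offset, and the log rate ratio moves by about 0.003 or less. Neither the trial's conclusion nor its power is threatened.

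The hospitalisation rate could be touched somewhat more. With an assumed 0.15 events per year and 25% of events followed by stopping drug, 8 to 14 of about 880 events would be lost (0.9% to 1.6%) and the log rate ratio would move by 0.007 to 0.012. Neither input comes from the documents, so this is only an illustration.

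**What to change.** In SAP 6.9, define time at risk for the primary analysis as (last dose + 1 day - first dose + 1) minus only those event days that come after the onset day and fall on or before last dose + 1 day. Each onset day stays at risk, so every offset is at least 1 day and no treated patient is lost. An event still open at last dose + 1 day is cut there and needs no end date.

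Replace the on-treatment label in SAP 6.9, and state that SAP 7.7 describes exposure for display only. Use the same rule in the observed-rate formula and the hospitalisation rate. In the sensitivity analysis, cut events at the end of the planned treatment period. Record the change as a clarification of protocol 7.3.1.

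The cost is a short SAP revision and one line of derivation code before unblinding, with no new data. Reported rates become slightly lower. Part of this is a choice of definition: keeping one onset day per event at risk adds about 0.85/365 = 0.2% to crude time at risk at the Tio 5 rate, and the fitted rate may fall by somewhat more.

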## **7.7 EXTENT OF EXPOSURE**

Extent of exposure to trial medication within the study will be displayed by treatment for the TS. Treatment exposure will be calculated as drug stop date - drug start date + 1 day. Both descriptive statistics and categorization by exposure intervals (e.g.  $\leq 90$  days, 91-180 days, 181-270 days, 271-360 days,  $\geq 361$  days) will be used.

The extent of observation time will be summarized similarly. The time intervals will be similar except for an additional category to account for the full follow-up period (i.e. 360 – 381 days and  $\geq 382$  days).

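### SAP 6.9 labels the exposure behind the primary rate with the wrong period name, gives no patient-level exposure for the offset, and drops the 365 from its rate formula (minor)

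*SAP*

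**What the plan says.** SAP 7.4 counts primary events within one window: "The exacerbation events will be only counted in this analysis if they occurred during the actual treatment period". SAP 6.1 fixes that window: "The actual treatment period is defined as the interval from first in-take of study medication until 1 day after last in-take of study medication". Table 6.1:2 agrees, assigning the primary exacerbation analysis to the actual treatment period.

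For the denominator, SAP 7.4 states "LOGDURS=log(exposure) as described in" section 6.9, and it points to the same section for the observed rate. Section 6.9 introduces its formula with "For the on-treatment analysis total exposure is calculated as follows". In SAP 6.1 that label has its own meaning: "The on-treatment period is defined as the interval from first in-take of study medication until 21 days after last in-take of study medication". Table 6.1:2 uses that period for the adverse event analysis only.

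Section 6.9 then gives two lines:
- Line 1 divides the sum of all patients' exposure by 365 to obtain patient-years.
- Line 2, the observed rate, divides the number of events by the summed exposure minus the summed event duration, with no 365.

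Two other sections contain day-counts. SAP 6.8 (time to event) gives patients without an event a time at risk of last dose minus first dose plus 1, plus 1 wash-out day. SAP 7.7 (exposure display) says: "Treatment exposure will be calculated as drug stop date - drug start date + 1 day".

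**The concern.** The primary endpoint is an annualised rate, so its denominator should be as exactly specified as its event count. It is not, in three respects.

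- **Label.** The section that the primary model refers to carries the name of a period 20 days longer than the window in which primary events count. Person-time in which no event can count would dilute the rate.
- **Level.** The offset is the logarithm of one patient's exposure. Section 6.9 gives only totals over patients, so it does not say how many days each patient contributes, in what unit, or how that patient's event days are removed.
- **Unit.** Line 1 shows that summed exposure is held in days. Line 2 uses the undivided sum, so under a heading about annualised rates it yields a daily rate.

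At stake are the per-arm annual rates and whether a second programmer would reproduce them.

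**Working it through.** **1. The plan's own figures.** SAP 6.9 states no numerical result. The planning figures that use annual rates are in protocol 7.6. Inputs: rates r1 = 0.85 and r2 = 0.748 per year, rate ratio 0.88, two-sided alpha 0.01, power 90%, dispersion k from 0.625 to 0.9, follow-up t = 1 year.

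n per arm = (2.5758 + 1.2816)² × [(1/t)(1/r1 + 1/r2) + 2k] / (ln 0.88)²

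| k | computed n | stated n | power at t = 0.85 | stated |
|---|---|---|---|---|
| 0.625 | 3426.7 | 3427 | 85.8% | 85.8% |
| 0.7 | 3563.3 | 3563 | 86.0% | 86.0% |
| 0.8 | 3745.4 | 3745 | 86.2% | 86.2% |
| 0.9 | 3927.5 | 3927 | 86.4% | 86.4% |

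The planning figures reproduce, and none of them depends on SAP 6.9.

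**2. Unit.** With exposure in days, line 2 returns 0.85/365 = 0.00233 and 0.748/365 = 0.00205. The ratio is still 0.88. In the model, multiplying every exposure by 365 shifts both log rates by ln 365, and the shift cancels in their difference.

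**3. Period, if on-treatment is read as SAP 6.1 defines it.** Treatment is planned for 360 days (SAP 6.1).
- Completer: 361/381 = 0.9475. The rates would read 0.85 × 0.9475 = 0.805 and 0.748 × 0.9475 = 0.709, or 5.3% low.
- Mean of 306 days on drug: (306 + 1)/(306 + 21) = 307/327 = 0.939. The rates would read 0.798 and 0.702, or 6.1% low. The 306 is 360 × 0.85. It is an assumption, because it treats the protocol's 15% loss of information in patient-years as lost treatment days.
- Removing an assumed 17 event days per patient from the 306-day case gives 290/310 = 0.935, or 6.5% low.

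**4. Rate ratio under the +21-day reading.** With equal mean exposure in the arms it stays at 0.88. With assumed mean exposures, to last dose + 1 day, of 280 days on tiotropium and 320 on the combination: 0.88 × (320/340)/(280/300) = 0.887. With 290 and 310 days: 0.88 × (310/330)/(290/310) = 0.884.

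**5. Simulation.** One negative binomial data set was fitted with each offset: 3900 per arm, k = 0.8, rates 0.85 and 0.748, about 16% stopping early with the same pattern in both arms (assumed).

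| Offset | Tio 5 | T+O 5/5 | Rate ratio | z |
|---|---|---|---|---|
| +1 day, years | 0.847 | 0.743 | 0.8770 | -3.843 |
| +1 day, days | 0.00232 | 0.00204 | 0.8770 | -3.843 |
| +21 days, years | 0.798 | 0.700 | 0.8776 | -3.826 |

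The z value is for the treatment difference, which the LSMEANS statement in SAP 7.4 requests. A joint test that both log rates are zero would depend on the unit (2-df Wald 194.5 in years, 129,022.5 in days). The reported p-value should therefore be the one for the difference.

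**6. The SAP 7.7 count.** Without the wash-out day, a completer has 360 instead of 361 days: 361/360 = 1.003, so rates would be about 0.3% high.

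**The case against.** The strongest reply is that no competent programmer would add 21 days. Section 6.9 contains no such term; it speaks only of exposure, which it leaves undefined. SAP 5.1, Table 6.1:2 and SAP 7.4 all name the actual treatment period for the primary analysis. Protocol 7.3.2 describes the efficacy analyses as on-treatment plus 1 day, which suggests that in the efficacy context the word simply means on drug. SAP 6.8 already contains the right day-count. A printed rate of 0.0023 would be noticed at once, and the asterisk on the word annualized in 6.9 may lead to a footnote, missing from the available text, that gives the unit.

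Most of this stands, and it rules out three stronger readings:
- **That the SAP puts last dose + 21 days into the primary denominator.** What is shown is a label that conflicts with a defined term, not a formula that uses the wrong period.
- **That the SAP holds three rival definitions of the primary denominator.** Section 6.9 gives no day-count, and 7.7 is written for the exposure table.
- **That the treatment comparison or the power is at risk.** Steps 1, 2, 4 and 5 of the working show otherwise.

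The reply does not remove the defect. The day-count in 6.8 is for time-to-event analyses and is not tied to the offset. Section 6.9 remains the place to which 7.4 sends the reader, and it defines no patient-level exposure. A footnote on the unit would answer the missing 365 only.

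**Conclusion.** The point holds as a minor specification error. As written, SAP 6.9 has a period label that contradicts SAP 6.1 and 7.4, no patient-level exposure for the offset, and a rate formula that is per patient-day unless the unseen footnote says otherwise.

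The consequence falls on the per-arm annual rates: a factor of 365 if line 2 is followed literally, and about 5% to 6% low if the label is taken as defined. The 5.3% figure for a completer follows from the SAP's own periods. The 6.1% rests on the assumed mean of 306 days, and the 6.5% also on the assumed event days. The documents give neither a discontinuation pattern nor event durations.

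The rate ratio, its 99% CI and the treatment-difference test do not depend on the unit. They hardly depend on the period: 0.877 against 0.878 in the simulation, and 0.88 to 0.887 under a deliberately unequal exposure assumption. Sample size and power do not change.

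**What to change.** In SAP 6.9:
- Replace the on-treatment label with the actual treatment period.
- Define each patient's exposure in years as [(last dose − first dose + 1) + 1 wash-out day − event days within that window] / 365, matching the day-count in SAP 6.8.
- Set LOGDURS to the logarithm of that quantity, and write the observed rate as events divided by the sum of the same patient-years.
- Say that the SAP 7.7 definition serves the extent-of-exposure table only.

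The cost is a few lines of SAP text and one programming check. Design, sample size and data collection are unaffected.
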